Appendix III ECOG Performance Status Scale

Grade	Description
0	Fully active, able to carry on all pre-disease performance without restriction
1	Restricted in physically strenuous activity but ambulatory and able to carry out work of light or sedentary nature—(eg, light housework or office work)
2	Ambulatory and capable of all self care, but unable to carry out any work activities; up and about $> 50\%$ of waking hours
3	Capable only of limited self-care, confined to bed or chair >50% of waking hours
4	Completely disabled; cannot carry out any self care; totally confined to bed chair
5	Dead

Source: Oken MM, Creech RH, Tormey DC, et al. Toxicity and Response Criteria of The Eastern Cooperative Oncology Group. *Am J Clin Oncol*. 1982; 5:649-655.

Appendix IV Research Biopsies and Blood Collection

Tissue Collection Guidelines for Snap Freezing Tissue for Storage

Tissue will be snap frozen according to the Biospecimen and Project Management Core (BPM) protocol. Briefly, immediately after biopsy, tissue will be placed in a screw-capped cryovial, and submerged in liquid nitrogen for rapid freezing and preservation of tissue. Tissue must be transported to the Core in the Baylor Charles A. Sammons Cancer Center on the 6th floor on dry ice. Tissue will then be stored in -80°C freezer until further use.

Blood Collection Guidelines

I. Collections at Clinical Site

a. Blood: Collect 4 tubes of whole blood in 10 mL purple-top EDTA hematology tubes (processing as soon as possible, <1 hour).

II. Further Processing

a. Buffy Coat isolation per BPM Core standard protocol, and store at -80°C as usual.

III. Kit contents

- 1. Four barcoded labels for 10 mL purple top EDTA hematology tubes
- 2. Four to 6 externally threaded cryovials with barcoded labels
- 3. Consent form

Appendix V Patient Diary for LY3023414 administration and Treatment Side Effects

Patient Diary

Patient:	
Dates:	to

LY3023414 should be taken twice a day, about 12 hours apart, every day. LY3023414 should be taken with food, although it is not required. You should take your study drug at about the same times each day, and not take more than what is prescribed. You must swallow the study drug whole and not chew it or open the capsule before swallowing. Keep out of reach of children and do not give to any other person. Store the bottle within the temperature range stated on the label.

When you take your study medication, write the date and time taken in each of the corresponding boxes. If you miss a dose of LY3023414, you should take the dose as soon as possible, but not less than 6 hours before the next dose is due. If the next dose is due within 6 hours, you should skip the missed dose and take the next dose as scheduled. Put an "X" in the appropriate boxes on a day that you did not take LY3023414 (missed dose). **TAKE YOUR NEXT DOSE AT THE NEXT SCHEDULED TIME.**

Please remember to bring the medication bottles and any remaining medication with you to your next study visit or as instructed by the study staff. Please also bring this diary.

On the second page, please record any side effect you think you may be having during treatment. Please show this diary to your study coordinator at each visit.

Dosing Diary:

Day of the Week:							
Date:	//		_/_/_	//		/	//
LY3023414 Dose:	mg	mg	mg	mg	mg	mg	mg
Dose Times AM							
PM							

Day of the Week:							
Date:	//	//	//	//	//	//	
LY3023414 Dose:	mg						
Dose Times AM							
 PM							

Side Effects Diary:

1 Nausea 6 Rash

Vomiting
Mouth Sores
Diarrhea
Fatigue
Other (specify)

5 Loss of Appetite

Side Effects	Day	Time(s)	Treatment	Time Taken	Result

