7.2 STUDY TREATMENT ADMINISTRATION

Patients will receive prexasertib as an approximately 60-minute infusion on Day 1 and Day 15 of a 28-day cycle. Oral LY3023414 will be administered twice a day (BID) on Days 1 to 28 of a 28-day cycle. On prexasertib dosing days, the administration of LY3023414 will follow immediately after the end of the prexasertib infusion (within 5 minutes) on Day 1 of each cycle. Patients should take the morning and evening doses of LY3023414 approximately 12 hours apart (preferably within a 10- to 14-hour range). Please refer to Sections 7.2.2.1 and 7.2.2.2 for further details.

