7.2.4.1 LY3023414 Dose Modifications

Dose reductions will be at the physician's discretion. Two dose reductions are permitted for LY3023414. Dose reductions beyond Level -2 would result in discontinuation of treatment. Reescalation to the previous dose is acceptable in the absence of continuing toxicity, provided that this dose is not greater than current dose being tested. If subsequent dose reduction is required after re-escalation, the patient must be maintained at the reduced dose level for all remaining cycles.

The dose reduction levels for LY3023414 are shown in Table 2.

Table 2. LY3023414 Dose Reduction Levels		
Level	LY3023414	
Starting Dose (Level 0)	150 mg Q12H	
Level -1	100 mg Q12H	
Level -2	100 mg Q24H	
Abbreviations: Q12H = every 12 hours; Q24H = every 24 hours		

Nonhematologic Toxicity:

For nonhematologic toxicities that are \leq grade 2, manage symptomatically if possible, and resume without dose reduction.

For nonhematologic Grade 3 or 4 toxicities (excluding nausea and alopecia), the treatment should be withheld until the patient recovers completely or to Grade 1 toxicity. This reduction should be permanent. If the treatment was withheld for more than 3 weeks, the patient will be taken off treatment.

Hematologic Toxicity:

Treatment decisions and dose reductions should be made based on ANC and platelet counts on the day of treatment administration. A reduction due to low hematologic values on the day of treatment is not permanent and is made on each treatment visit. Dose modifications must be recorded on the CRF.

- Patients must have ANC of ≥1000/mm³ on Day 1 of each cycle (if pegfilgrastim is being used) or of ≥1200/mm³ on Day 1 (if no pegfilgrastim is being used) to receive scheduled treatment. Treatment may be delayed to allow sufficient time for recovery.
- Patients must have a platelet count of ≥75,000/mm³ on Day 1 of each cycle to receive scheduled treatment. LY3023414 should be delayed until platelet counts recover to ≥75,000/mm³ and then treated with either full dose or reduced dose at the physician's discretion. Treatment may be delayed to allow sufficient time for recovery.

Use of hematopoietic growth factors to ameliorate hematologic toxicity is at the discretion of the physician investigator and guidance from Eli Lilly.

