8.2 ASSESSMENTS DURING TREATMENT

The following assessments will be performed during therapy on Day 1 prior to the start of each cycle, unless otherwise specified. A Cycle is defined as 28 days (prexasertib dosing on Day 1 and 15).

There is a window (**up to 4 calendar days prior to the scheduled time point**) for assessments during the study. Any delay within this window is NOT a deviation. Assessments that are to be done on days when study drug is administered must be done **prior to dosing** as these assessments (CBC, CMP, assessment of response, etc) may determine whether or not drug is administered, or if a dose reduction is necessary, unless otherwise noted.

Note for Cycle 1 only: the prestudy assessments that correspond to assessments below may be used as Cycle 1 assessments as long as they are completed within the 72 hours prior to the patient receiving their first dose of study drug. If more than 72 hours have elapsed since the prestudy assessment, the assessment must be repeated for Cycle 1.

- 1. A brief medical history, to capture events that have occurred since the last cycle. Events that were not captured in the baseline complete medical history should be recorded on the AE page of the CRF.
- 2. A brief physical examination, including vital signs and body weight
- 3. ECOG PS (Appendix III)
- 4. Assessment of concomitant medications
- 5. A CBC with differential and platelet count on Day 1 and Day 15 of every cycle
- 6. A CMP Day 1 and Day 15 of each cycle
- 7. Assessment of magnesium (Mg) and phosphorus (P) Day 1 and Day 15 of each cycle
- 8. HbA1c must be obtained Day 1 and Day 15 of each cycle
- 9. Fasting serum glucose must be obtained Day 1 and Day 15 of each cycle
- 10. A pre-dose ECG (within 10 minutes of beginning prexasertib infusion) must be obtained on Cycle 1 and Cycle 2. Additional ECG may be obtained if clinically indicated.
- 11. A post-dose ECG (within 10 minutes of ending prexasertib infusion) must be obtained on Cycle 1 and Cycle 2. Additional ECG may be obtained if clinically indicated. **NOTE:** it is

- preferred to complete the post-dose ECG upon completion of the prexasertib infusion, but prior to LY3023414 dosing.
- 12. Tumor response by clinical assessment of the patient's disease (ie, by physical examination)

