- 13. Radiological assessment of tumors (ie, chest and abdomen CT scan) every 8 weeks or as clinically indicated. The methods used for prestudy assessments should be used throughout the study. If possible, the same equipment should be used each time.
- 14. Assessments of other sites of disease must be performed **only to confirm a CR**.
- 15. Toxicity
- 16. If safely accessible, research biopsies of the same metastatic lesion (or different metastases if the initial metastasis has regressed) may be obtained **any time after the completion of Cycle 2 of the treatment combination, or at the physician's discretion**. If a research biopsy from a patient's metastatic disease cannot be safely obtained, a skin biopsy is permitted.
- 17. Whole blood collection (40 mL) for germline exome sequencing studies any time after the completion of Cycle 2 of the treatment combination, or at the physician's discretion.
- 18. Patient diary assessment of LY3023414 dosing and treatment adverse events

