8.3 OFF TREATMENT/END OF TREATMENT ASSESSMENTS

This is a single assessment that will be performed within 30 days \pm 2 days when a patient finishes treatment or goes off treatment because of PD, toxicity that places patients off treatment, if patients achieve a confirmed clinical complete response, or in cases of physician decision or where patient withdraws consent. Patients who withdraw consent may not want any further assessments; however, they should be encouraged to have these final assessments done.

NOTE: End of treatment, or off treatment, is NOT considered off study or withdrawn from the study.

The following evaluations will be performed at this visit:

- 1. A brief medical history should be done to capture events that have occurred since the last cycle. Events that were not captured in the baseline complete medical history should be recorded on the AE page of the CRF.
- 2. A brief physical examination, including vital signs and body weight.
- 3. A CBC with differential and platelet count.
- 4. A CMP
- 5. A serum pregnancy test
- 6. A tumor clinical assessment of the patient's disease (ie, by physical examination)
- 7. A toxicity assessment
- 8. Collection of any outstanding patient diaries

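### The patient diary prints a fixed twice-daily LY3023414 instruction, which is wrong at dose Level -2 (100 mg Q24H)

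*Combined protocol and SAP*

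**What the plan says.** Section 7.2.4.1 governs LY3023414 dose changes. It states that "Two dose reductions are permitted for LY3023414" and that "Dose reductions will be at the physician's discretion". Table 2 gives three levels: 150 mg Q12H (Level 0), 100 mg Q12H (Level -1) and 100 mg Q24H (Level -2). Treatment stops only if a reduction below Level -2 is needed, so a patient at Level -2 remains on drug and keeps using the diary.

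Appendix V is the only diary in the document. It instructs: "LY3023414 should be taken twice a day, about 12 hours apart, every day". Nothing makes that sentence depend on dose level. The dosing grid has a blank mg field for each day and an AM and a PM time row, and patients are told: "When you take your study medication, write the date and time taken in each of the corresponding boxes". The same page cautions patients not to exceed their prescription, and asks them to show the diary to the coordinator and bring back remaining drug at visits.

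On monitoring, Section 7.2 says "Patients will receive prexasertib as an approximately 60-minute infusion on Day 1 and Day 15 of a 28-day cycle", and Section 8.2 requires "A CBC with differential and platelet count on Day 1 and Day 15 of every cycle". Section 8.2, item 18, also lists "Patient diary assessment of LY3023414 dosing and treatment adverse events", and Section 8.3 adds "Collection of any outstanding patient diaries".

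**The concern.** Levels -1 and -2 use the same 100 mg dose and differ only in how often it is taken. The diary lets staff change the amount but not the frequency. A correctly completed form would read 100 mg at either level, so it would not tell the patient that the second reduction had happened.

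Other parts of the form also lean towards two doses a day. Each day has two time rows, and a dose not taken is to be marked as missed. Section 7.2.2.1 limits the six-hour missed-dose rule to BID dosing, but the diary repeats the rule without that limit. Nothing tells a Level -2 patient that one of the two boxes should stay empty.

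What is at stake is dosing safety in a patient whose drug has already been cut twice. Following the printed instruction would put that patient back on the level just judged too high.

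**Working it through.** The plan gives no figure to reproduce. The check compares Appendix V with Table 2 and then works out daily dose as mg per dose × doses per day.

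**Assigned dose (Table 2) against the diary's frequency (Appendix V)**

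| Level | Assigned | Assigned daily dose | Daily dose at two doses a day | Agree? |
|---|---|---|---|---|
| 0 | 150 mg Q12H | 2 × 150 = 300 mg | 300 mg | Yes |
| -1 | 100 mg Q12H | 2 × 100 = 200 mg | 200 mg | Yes |
| -2 | 100 mg Q24H | 1 × 100 = 100 mg | 2 × 100 = 200 mg | No |

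At Level -2 the diary gives 200/100 = 2 times the assigned dose. Relative to the starting dose, the assigned intake is 100/300 = 33% and the diary intake is 200/300 = 67%, the same as Level -1.

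**How long an error could run before a scheduled check**

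Infusions and blood counts fall on Days 1 and 15, so visits are 15 − 1 = 14 days apart. The diary is to be shown at each visit, and its two seven-day grids cover 2 × 7 = 14 days. Over 14 days:

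- Assigned: 14 × 100 = 1,400 mg (14 doses)
- Diary text: 14 × 200 = 2,800 mg (28 doses)
- Excess: 2,800 − 1,400 = 1,400 mg (14 doses)
- Starting dose, for scale: 14 × 300 = 4,200 mg

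A longer interval can also be read from the plan. Section 8.2 places assessments on Day 1 of each cycle unless stated otherwise. Its diary item names no Day 15, and the diary row in Appendix II carries no Day 15 footnote. If the diary is checked only once per 28-day cycle, the excess is 28 × 200 − 28 × 100 = 2,800 mg (28 doses).

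Both figures are upper limits. They assume that the patient follows the printed frequency throughout and has enough drug, and the documents give no dispensing quantity.

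**The case against.** The strongest reply is that the diary simply repeats the standard regimen. Section 7.2, Table 1 and Section 7.2.2.1 all describe twice-daily dosing without mentioning dose level, and Section 7.2.4.1 then modifies it for individual patients. On that view the diary is an unadapted template rather than a contradiction. This holds for the protocol body, where staff read the sections together. It does not hold for the diary, because the patient sees that page and not Section 7.2.4.1.

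Second, the diary warns against taking more than prescribed, and a second daily dose at Level -2 would breach that warning. This lowers the risk. It also leaves the patient with two printed instructions that disagree, and the one that states a frequency is the wrong one.

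Third, harm needs a chain of events: two discretionary reductions, a patient who follows the form over the physician's current instruction, and enough surplus drug. Labels and staff instructions may well give the right frequency, although the documents do not reproduce them. The AM and PM boxes and the drug return would reveal doubled intake, but only afterwards. All of this stands and is why the practical weight is low. It is also fair that this is an inconsistency in a patient form and not a flaw in the trial's design.

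**Conclusion.** The point holds. At Level -2, a permitted on-treatment dose, the printed frequency is wrong and would double the assigned daily dose from 100 mg to 200 mg. At Levels 0 and -1 the diary is correct.

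The excess is at most about 1,400 mg over 14 days, or 2,800 mg if diaries are checked only at the start of each cycle. Both figures assume full adherence to the printed line and sufficient supply. Intake would equal Level -1 and would not exceed the starting dose. The number of patients who will reach Level -2 is not given and could be 0 of 10. There is no effect on the response endpoint, the sample size or any analysis. This is a minor patient-safety wording error that should be corrected because it is clear and cheap to fix.

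**What to change.** Leave Table 2 as it is. In Appendix V, replace the fixed frequency with a line that site staff complete, for example: take ___ mg, ___ time(s) a day. Alternatively, add a separate once-daily diary for Level -2 with a single time row per day. Issue the corrected form at every LY3023414 dose change, including any re-escalation allowed by Section 7.2.4.1.

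The cost is one revised patient form with IRB approval. Dose levels, visits and analysis do not change.

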7.2.2.1 LY3023414

Doses are administered orally BID approximately 12 hours apart (preferably within a 10- to 14-hour range) on Days 1 through 28 of each 28-day cycle. LY3023414 capsules should be taken at approximately the same time on each dosing day. LY3023414 may be administered with or without food. Patients may experience improved GI tolerability of LY3023414 when it is taken with or just after a meal. Patients should also be monitored in order to detect and treat mucositis/stomatitis early before it becomes severe.

On prexasertib dosing days, patients will receive prexasertib first (see Section 7.2.2.2). The administration of LY3023414 will follow immediately at the end of the prexasertib infusion (within 5 minutes of infusion end).

If the patient misses a dose of LY3023414, the patient should take the dose as soon as possible, but not less than 6 hours before the next dose is due for BID dosing. If the next dose is due in less than 6 hours, the patient should skip the missed dose and take the next dose as scheduled.

LY3023414 should be stored within the temperature range stated on the label. Patients should be instructed to store the drug product at home in the provided container and to keep out of the reach of children. The drug product should not be crushed or dissolved. Capsules should not be opened.²⁶

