7.2.2.2 Prexasertib

Prexasertib is administered as an IV infusion over 1 hour using a central or free-flowing peripheral IV line with an appropriate filter. Prexasertib should not come in contact with normal saline; the infusion line should be flushed with dextrose 5% injection before and after prexasertib administration.

On prexasertib dosing days, patients will receive prexasertib first. The administration of LY3023414 will follow immediately at the end of the prexasertib infusion (within 5 minutes of infusion end).

There is a low incidence of infusion reactions: In the event of a suspected infusion-related reaction, institutional guidelines for managing infusion reactions should be followed. For subsequent infusions, premedication with diphenhydramine and/or other premedication (see

Section 7.2.1) may be administered at the physician's discretion. The infusion rate may also be decreased by up to 50% after recovery from the infusion-related reaction. The patient should be monitored for signs and symptoms indicative of an infusion-related reaction.

The actual doses of prexasertib to be administered are determined by calculating the BSA for each patient at the beginning of each cycle.²⁷

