- 15. A clinical assessment of the patient's disease (ie, by physical examination) must be performed within 4 weeks prior to registration.

- 16. Radiological assessment of tumors (ie, chest and abdomen CT scan) must be performed within 8 weeks prior to registration. The methods used for prestudy assessments should be used throughout the study. If possible, the same equipment should be used each time.
- 17. Assessments of other lesions by physical exam must be performed within 4 weeks prior to registration.
- 18. If safely accessible, research biopsies of the patient's metastatic locoregional or pulmonary or hepatic disease must be obtained **prior to the first day of treatment**. If a research biopsy from a patient's metastatic disease cannot be safely obtained, a skin biopsy is permitted. If a skin biopsy cannot be safely obtained, patients may still be eligible, per physician discretion.
- 19. Whole blood collection (40 mL) for germline exome sequencing studies.
- 20. Distribution of LY3023414 dosing and treatment adverse events patient diaries (see Appendix V).

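### The patient diary leaves out the infusion-day rule for LY3023414, so a patient with an early routine who follows it can take one dose before the infusion and before that visit's checks.

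*Combined protocol and SAP*

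**What the plan says.** **What staff are told.** Section 7.2 sets the schedule: "Oral LY3023414 will be administered twice a day (BID) on Days 1 to 28 of a 28-day cycle", with prexasertib infused over about an hour on Days 1 and 15. Section 7.2.2.1 gives the order: "On prexasertib dosing days, patients will receive prexasertib first". It and Section 7.2.2.2 then require LY3023414 within 5 minutes of the infusion ending. Section 8.2 wants drug-day assessments finished before dosing, because they can decide whether drug is given or reduced. Section 7.2.4.1 bases LY3023414 decisions on neutrophil and platelet counts from the day of treatment and has low-count reductions made at each treatment visit. Section 8.2 also calls for an ECG just before and just after the infusion in Cycles 1 and 2, the second preferably before LY3023414.

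**What the patient is told.** Section 8.1, item 20, provides for prestudy "Distribution of LY3023414 dosing and treatment adverse events patient diaries". The diary in Appendix V says: "LY3023414 should be taken twice a day, about 12 hours apart, every day". It adds: "You should take your study drug at about the same times each day, and not take more than what is prescribed". On visits it says: "Please remember to bring the medication bottles and any remaining medication with you to your next study visit". On late doses it says: "If the next dose is due within 6 hours, you should skip the missed dose and take the next dose as scheduled". It does not mention prexasertib, infusion days or waiting.

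**The concern.** The diary carries over most of the patient-facing content of Section 7.2.2.1: the 12-hour spacing, the regular clock time, the 6-hour missed-dose rule, storage and unopened capsules. The infusion-day paragraph is not carried over, which looks like an oversight rather than a choice.

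The result is a handout that, followed to the letter, can make a patient break the protocol's own dosing order. The dose at stake is 150 mg, or 100 mg after a reduction. It could be taken on a morning when the visit would have led staff to hold or reduce it. Section 1.5 lists neutropenia and thrombocytopenia among the commonest events with the combination and reports a higher incidence than with either drug alone, so the count check has a purpose.

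**Working it through.** The plan gives no figure on this point. The check compares the texts and then counts doses.

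**1. When the conflict arises.** It arises whenever the patient's usual morning time is earlier than the infusion start. The documents give no clinic or home times, so these are assumptions:
- Routine at 05:00 to 07:00, infusion starting 08:00 to 11:00: the dose falls 1 hour (07:00 against 08:00) to 6 hours (05:00 against 11:00) before the infusion starts.
- Routine at 09:00 or 10:00, infusion starting 08:00: the dose does not precede the infusion.

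Only the morning dose is exposed, so the most is one dose per infusion day.

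**2. What that dose would precede.**
- *Assessments in 8.2 and the count decision in 7.2.4.1:* yes, unless they were done earlier under the window of up to 4 calendar days in 8.2.
- *Pre-infusion ECG:* yes. It is tied to the 10 minutes before the infusion, so the 4-day window does not help.
- *Post-infusion ECG:* yes, though its order relative to LY3023414 is only a preference.

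**3. Ceiling per cycle.** Inputs: 28-day cycle and two infusion days (7.2); dose levels (7.2.4.1, Table 2).
- Twice daily (Levels 0 and -1): 2 × 28 = 56 doses; 2/56 = 3.6%.
- Level -2 (100 mg once daily), if taken in the morning: 2/28 = 7.1%.

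**4. Context.** CBCs are scheduled only on Days 1 and 15, which carry 4 of the 56 doses. The other 52 (52/56 = 92.9%) fall on days with no scheduled count, by design. The diary can move 2 of those 4 ahead of the count.

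**5. Ceiling over time.** Assume Cycle 1 Day 1 is safe because no home routine exists yet. Over k cycles of twice-daily dosing the maximum is 2k − 1 doses.
- k = 2: 3 of 112 (2.7%).
- k = 6: 11 of 336 (3.3%).
- Full participation: the Synopsis and Section 8.4 cap it at 18 months from the start of treatment, about 548 days. With infusions every 14 days from Day 1, (548 − 1)/14 = 39.07, so 39 + 1 = 40 infusion days. Less Cycle 1 Day 1, that is 39 doses per patient, or 39 × 10 = 390 in ten patients.

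**6. Lower end.** The first possible error is Cycle 1 Day 15. The diary records dose times and asks the patient to show it to the coordinator at each visit, and Section 8.2, item 18, includes diary assessment. If staff see the error and correct it then, the count is 1 per patient, at most 10 in the trial. If staff explain the rule beforehand, it is 0.

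**7. ECGs.** With Cycle 1 Day 1 set aside, only Cycle 2 is exposed: one pair per patient, at most 10 pairs.

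**The case against.** The strongest reply is that the protocol is not defective on dosing order. Staff have the rule in three places, the 5-minute requirement already makes the infusion-day dose a clinic event, and patients bring their bottles. The diary is mainly a record, and its review gives staff an early chance to catch a mistimed dose. Consent pages, labels and oral instructions cannot be seen here and may carry the rule. Most doses follow no same-day count anyway, and Section 1.5 reports combination pharmacokinetics consistent with each drug alone. The documents give no pharmacologic reason for the order.

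Most of this stands, and it keeps the point small. It does not remove it. Bringing the bottles makes clinic dosing possible but does not tell the patient to wait. If the rule is given elsewhere, the diary still contradicts it.

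A reader might infer that patients are in fact left uninformed and will repeat the error every two weeks. The documents do not support that, because they do not show what staff say and they do provide for diary review.

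A reader might also infer that Day 15 lacks a same-day check, since the listed count thresholds in Section 7.2.4.1 are worded for Day 1. That is not supported either: the same section bases decisions on counts from the day of treatment at each treatment visit, and Section 7.2.4 applies its criteria at every clinic visit.

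**Conclusion.** The point holds as a minor operational and safety correction. The diary conflicts with the stated infusion-day order, and a patient with an early routine who obeys it can take one dose too soon. The per-cycle ceiling follows from the schedule. The 39-dose ceiling further assumes that all 18 months are spent on treatment, that the patient's routine always precedes the infusion, and that nobody corrects it. The real number should be far below that and may be 0.

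Two larger readings should be set aside. Because treatment continues to progression or unacceptable toxicity, a reader might infer that exposure has no limit, but the participation cap sets one. A reader might also infer a threat to the efficacy result. Nothing in the documents links the order of one morning dose to tumour response, and neither the response rate nor the 2-of-10 rule is affected.

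**What to change.** Add to the diary: *On infusion days (Day 1 and Day 15) do not take your morning dose at home; bring your drug and take it when staff tell you, right after the infusion; staff will tell you when to take your evening dose.*

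As an editorial alignment only, extend the sequence sentence in Section 7.2, which names Day 1 of each cycle, to Day 15 so that it matches Sections 7.2.2.1 and 7.2.2.2.

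The cost is IRB review of the revised diary and the changed phrase; no procedure is added. The downside is a longer gap before that day's first dose, which the 5-minute rule already implies. With an assumed 07:00/19:00 routine:

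| Infusion ends | Hours since last dose | Hours to usual evening dose |
|---|---|---|
| 09:00 | 14 | 10 |
| 11:00 | 16 | 8 |
| 13:00 | 18 | 6 |

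The later two rows fall outside the preferred 10- to 14-hour spacing. If the infusion ends after 13:00, less than 6 hours remain, and a patient applying the diary's missed-dose rule would skip the dose that the protocol requires. That is why staff should set the evening time.
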